7. HANDLING OF MISSING VALUES

Missing data will be handled based on the nature of the endpoint and the proposed statistical methods for analyzing the data.

For all endpoints that include seizure rate, days with missing seizure diary data will be subtracted from the seizure rate calculations. If seizure rate for any phase cannot be calculated for a subject due to missing information, the endpoint that involves seizure rate during that phase will be also missing for that subject.

For scales used in this study, scores will be imputed according to the imputation rules and algorithms for missing component scores that are provided in the data standard documents. Partial dates for AEs and concomitant medications will be imputed according to Pfizer standard algorithms.

The assessment of missing data for the primary endpoint will require the construction of the following windows and drop-out categories:

- *Windowing for each subject will be constructed for the 1st month, 2nd month, and 3rd month the subject was in the study. Thus a 28-day seizure rate will be determined for each windowed month for which seizure data exist, otherwise the seizure data will be considered missing with a corresponding reason for it being missing. Specific details are provided in [Appendix 3](#).*
- *Drop-out patterns will be constructed based on the reason the seizure data is missing for the corresponding windowed month. Hence, the following drop-out patterns will be defined for three specific categories of related to lack of efficacy or adverse event or other reason:*
 - *Completed study as planned.*
 - *Drop-out due to lack of efficacy:*
 - *Drop-out at month 1 due to lack of efficacy;*
 - *Drop-out at month 2 due lack of efficacy;*
 - *Drop-out at month 3 due to lack of efficacy.*
 - *Drop-out due to an adverse event:*
 - *Drop-out at month 1 due to an adverse event;*
 - *Drop-out at month 2 due to an adverse event;*
 - *Drop-out at month 3 due to an adverse event.*
 - *Drop-out due to other reason:*
 - *Drop-out at month 1 due to other reason;*
 - *Drop-out at month 2 due to other reason;*
 - *Drop-out at month 3 due to other reason.*

Other reason includes any drop-outs excluding efficacy and adverse event.

These drop-out patterns will be summarized by treatment group to assess any imbalance using frequency counts. If there is a significant amount of missing data, then multiple imputation techniques will also be applied to the primary analysis model. However, if the amount of missing data is not significant (ie, less than 5% across all treatment groups),

then the assessment of missing data will not include multiple imputation techniques applied to the primary analysis model.

Further details regarding the statistical strategy of assessing missing data will be provided in Appendices [Appendix 4](#), [Appendix 5](#), and [Appendix 6](#).

8. STATISTICAL METHODOLOGY AND STATISTICAL ANALYSES

The ITT population will be used in the analyses of the primary efficacy endpoint, and for all other efficacy endpoints. The Safety population will be used in the analyses of the safety data.

8.1. Analysis of Primary Efficacy Endpoint

The primary efficacy analysis of the primary endpoint, $\log_e(28\text{-days seizure rate}_t + 1)$ as defined in [Section 6.1](#) of this document, will utilize a linear model with the following fixed effect terms:

- A \log_e transformed baseline seizure rate $\log_e(28\text{-days seizure rate}_b + 1)$ for all PGTC seizures, as a continuous covariate;
- Age strata (Stratum 1: 5-7 years of age; Stratum 2: 8-11 years of age; Stratum 3: 12-16 years of age; Stratum 4: 17-65 years of age);
- Geographic region (See [Section 6.4](#)) by pooling of investigator centers;
- Treatment group [placebo, Dose Level 1: pregabalin 5 mg/kg/day (maximum 300 mg/day), Dose Level 2: pregabalin 10 mg/kg/day (maximum 600 mg/day)].

There will be two pair-wise comparisons of interest:

- 1) Dose Level 2: pregabalin 10 mg/kg/day (maximum 600 mg/day) - placebo, and
- 2) Dose Level 1: pregabalin 5 mg/kg/day (maximum 300 mg/day) - placebo.

The difference in the least squares means and their standard errors for these two pair-wise comparisons will be used for constructing test statistics and two sided 95% confidence intervals.

Each dose of pregabalin will be compared to placebo in a pair-wise manner using a sequential step-wise testing procedure to control for multiplicity of testing such that the experiment-wise type I error rate will not exceed the 5% level of significance:

1. The first step will test the null hypothesis of equal treatment effect of Dose Level 2 vs. placebo at $\alpha=0.05$ 2-sided for the primary endpoint.

If the null hypothesis of the first step is rejected, then proceed to the second step, otherwise accept the null hypothesis of the first step, stop further testing, and claim no treatment effect.

2. The second step will test the null hypothesis of equal treatment effect of Dose Level 1 vs. placebo at $\alpha=0.05$ 2-sided for the primary endpoint.

If the null hypothesis of the second step is rejected, then claim a treatment difference for both dose groups of pregabalin [Dose Level 2: 10 mg/kg/day (maximum 600 mg/day) and Dose Level 1: 5 mg/kg/day (maximum 300 mg/day)] from the placebo group for the primary endpoint only; otherwise accept the null hypothesis of the second step, stop further testing, and claim a treatment difference for only pregabalin Dose Level 2: 10 mg/kg/day (maximum 600 mg/day) from placebo for the primary endpoint only.

The difference in the least squares means and their standard errors for these 2 pair-wise comparisons will be used for constructing test statistics and 2-sided 95% confidence intervals. Results will be reported as “percent reduction in seizures from baseline” relative to placebo. For example, a difference between 1 of the pregabalin doses and placebo of -0.358 on the log-transformed scale for the 28-day seizure rate, translates into a 30.1% reduction in the 28-day seizure rate of the pregabalin group from the placebo group (ie, $100\% * [\exp^{-0.358} - 1] = -30.1\%$).

An additional back transformation will be calculated for percent reduction in seizures for each pregabalin treatment group relative to placebo for presentation as follows:

$$100\% \times \frac{[\exp(\text{LSMean(pregabalin)}) - 1] - [\exp(\text{LSMean(placebo)}) - 1]}{\exp(\text{LSMean(placebo)}) - 1}$$

The 28-day seizure rate of log scale in the double-blind treatment phase will be summarized by each month and the entire 12-weeks double-blind period for each treatment group, age group [pediatrics overall (<17 years) and adults (17-65 years)], and geographic region.

Contingency plan for the primary ANCOVA analysis model

If after unblinding, the primary ANCOVA analysis model as described above performs well without any issues, the primary analysis model will stay as described above. However, in case of ANCOVA analysis issues, for example, with convergence or missing cells in a particular treatment within a region or within an age strata, the cause of the analysis model issues will be mitigated, for example, as follows:

- If a small region, say US region, causes the model issue alone, the small region (say US region) will be pooled with European Union; Other ANCOVA model terms will stay as is;
- If age strata causes the model issue alone, the age group (5-16 years of age and 17-65 years of age) as described in [Section 6.4](#) will be used instead of the age strata; Other ANCOVA model terms will stay as is;

- If both a small region and age strata cause the model issue, then ANCOVA analysis will be performed with the small region (say US region) pooled with European Union and age group (instead of age strata), Other ANCOVA model terms will stay as is.

Other analyses of continuous dependent variables with ANCOVA model will follow the same procedure as the primary efficacy endpoint analysis. Responder rates and any other binary variables that use the same planned model as primary efficacy endpoint analysis will similarly be adjusted as needed.

Sensitivity Analysis

As a sensitivity analysis of the primary endpoint, multiple imputation methods will be used to evaluate the impact of missing data (See [Appendix 4](#)).

Subjects who discontinue the study for insufficient clinical response, adverse event, or death will be imputed based on the observed placebo distribution, regardless of randomized treatment assignment. Imputation will be based on baseline $\log_e(28\text{-days seizure rate}_b + 1)$, geographical region, baseline weight (continuous), and age strata.

Subjects who discontinue the study for other reasons, or who complete the study but have a missing double blind seizure rate, will be imputed based on observed subjects in the same randomized treatment group. Imputation will be based on treatment group, baseline $\log_e(28\text{-days seizure rate}_b + 1)$, geographical region, baseline weight (continuous), and age strata.

A sensitivity analysis will be performed using the same linear model as the primary efficacy analysis except for the age covariate, which will be applied for the 2 age groups (5-16 years of age; 17-65 years of age).

An additional sensitivity analysis will be performed using the same linear model as the primary efficacy analysis with two age groups covariate as well as pooled region of US and European Union.

A ranked ANCOVA will be performed for the change from baseline to double blind phase of log-transformed (\log_e) 28-day seizure rate for all PGTC seizures, including age strata, treatment group, and region.

A Wilcoxon-Mann Whitney test will also be performed and reported for the change from baseline to double blind phase of log-transformed (\log_e) 28-day seizure rate for all PGTC seizures.

Supplemental Analysis

A supplemental analysis will be performed to investigate generalizability of the treatment difference with respect to the 2 age categories (ie, a possible treatment-by-age interaction that is statistically and clinically relevant). The estimated seizure rate, standard error and the corresponding 95% confidence interval in addition to the treatment difference between each pregabalin treatment group and placebo will be calculated for both pediatric (5-16 years of age) and adult population (17-65 years of age). This supplemental analysis will also be a re-evaluation of the primary analysis model with an interaction term for treatment-by-age. This model will not replace the primary model.

As a supplemental analysis, a generalized linear model assuming a Poisson and negative binomial distributions and canonical log link function will be applied to the raw seizure counts.^{1,2} The model will have an off-set parameter for the amount of time (i.e., $\log_e(\text{days})$) the subject was in the double blind treatment phase. A scale parameter of Pearson will be specified to fit the Poisson distribution.

The analyses with Poisson and negative binomial models will be performed with baseline seizure count as covariate.

The raw 28-day seizure rate will be summarized overall, and separately by age group of pediatrics overall (<17 years) and adults (17-65 years).

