2.2. Statistical Power and Sample Size

A total sample size estimate of 168 subjects allows for the evaluation of efficacy using the primary endpoint, $\log_e(28\text{-day seizure rate} + 1)$, for making comparisons between placebo vs. 5 mg/kg/day pregabalin (maximum 300 mg/day; Dose Level 1), and placebo vs. 10 mg/kg/day (maximum 600 mg/day; Dose Level 2) pregabalin groups for the treatment period of the study. The following sample size assumptions and corresponding power calculations are provided in Table 1 below. This sample size will also allow for a general assessment of safety and tolerability.

Table 1. Power Calculations and Sample Size Assumptions with 56 Subjects per Group for the Primary Endpoint (\log_e (28-day seizure rate + 1))

Comparison	Log Transformed Difference from Placebo	Percent Difference from Placebo	SD (log transformed 28 day seizure rate)	Power
Expected difference ¹ between 600 mg/day and placebo	-0.534	-41.4%	0.73 0.67	0.970 0.984
Expected difference ¹ between 300 mg/day and placebo	-0.358	-30.1%	0.73 0.67	0.742 0.800

¹ Expected difference is 80% of the observed difference between the specified pregabalin dose minus placebo based on a meta-analysis of Studies 1008-009, 1008-011, and 1008-034 based on the log transformed 28 day seizure rate, with 300 mg/day only in Study 1008 -034.

The primary statistical analysis will model the log transformed 28 day seizure rate, and compare each dose of pregabalin to placebo in a step-wise manner, starting with the highest dose of pregabalin. Since there is a significant dose response of pregabalin, the power to detect expected differences for each pregabalin dose relative to placebo will be different. Hence, this step-wise testing procedure will provide maximum power as well as control for multiplicity of testing at the desired 0.05 level of significance for the primary analysis.

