6. ENDPOINTS AND COVARIATES

6.1. Efficacy Endpoint(s)

For all 28-day log seizure endpoints, the results will be reported as “percent reduction in seizures” relative to placebo. For example, a difference between one of the pregabalin doses and placebo of -0.400 on the log transformed scale for the 28-day seizure rate translates into a 33% reduction in the 28-day seizure rate of the pregabalin group from the placebo group (ie, $100\% \times [\exp(-0.400) - 1] = -33\%$). The “percent reduction in seizures” will be calculated for changes versus placebo on the following statistics: the two-sided 95% confidence intervals, the least square means and their standard errors.

An additional back transformation will be calculated for percent reduction in seizures for each pregabalin treatment group relative to placebo for presentation as follows:

$$100\% \times \frac{[\exp(\text{LSMean(pregabalin)}) - 1] - [\exp(\text{LSMean(placebo)}) - 1]}{\exp(\text{LSMean(placebo)}) - 1}$$

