6.1.1. Primary Endpoint

The primary endpoint will be the log-transformed (\log_e) 28-day seizure rate for all PGTC seizures collected during the double-blind assessment phase (not including the 1-week double-blind taper phase). The 28-day seizure rate will be calculated as follows for the double-blind assessment phase:

$$\text{28-day seizure rate} = \frac{\# \text{ of seizures in the double-blind assessment phase of study}}{\lceil \# \text{ of days in period} - \# \text{ of missing diary days in period} \rceil} \times 28$$

When the log-transformation is used, the quantity “1” is added to the 28-day seizure rate for all subjects to account for any possible “0” seizure incidence. This will result in the following primary efficacy endpoint: $\log_e(28\text{-day seizure rate} + 1)$.

The 28-day seizure rate for all PGTC seizures collected during the baseline phase will be calculated similarly.

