Appendix 1. Data Derivation Details

This table describes how seizure related endpoints have been defined.

Endpoint	Derivation
8-week baseline phase (b) 28-day seizure rate	28-day seizure rate _b = [(# of seizures _b) ÷ (#of days _b - # of missing diary _b)] × 28, where #of days _b is defined as (first dose date-1) – screening date +1.
12-week double-blind treatment phase (t) 28-day seizure rate	28-day seizure rate _t = [(# of seizures _t) ÷ (#of days _t - # of missing diary _t)] × 28, where #of days _t is defined as date of last dose in phase – date of first dose in phase +1.
Primary endpoint : Log _e of 28-day seizure rate during 12-week double-blind treatment phase	Log _e (28-day seizure rate _t +1)
“Percent reduction in seizures” relative to placebo	
For example, a difference between one of the pregabalin doses and placebo of -0.400 on the log transformed scale for the 28-day seizure rate translates into a 33% reduction in the 28-day seizure rate of the pregabalin group from the placebo group (ie, 100%*[exp-0.400-1] = -33%)
 
An additional back transformation will be calculated for the percent reduction in seizures for each pregabalin treatment group relative to placebo for presentation in the CSR as follows:
 $100\% \times \frac{\exp(\text{LSMean(pregabalin)}) - 1 - [\exp(\text{LSMean(placebo)}) - 1]}{\exp(\text{LSMean(placebo)}) - 1}$
Percent change from baseline in 12-week 28-day seizure rate	% Change = [28-day seizure rate _t - 28-day seizure rate _b] / 28-day seizure rate _b] × 100%
Responders	
≥50% reduction in the 28-day seizure rate from baseline during the 12-week double-blind treatment phase, then response = 1 (responder) otherwise response = 0 (non-responder).
 
The response status will be set as missing if the baseline seizure rate is missing. If baseline seizure rate is non-missing but there are no double-blind phase seizure rates, then the response status will be set as non-response

Proportion Seizure-free days	The numerator for seizure-free days is defined as the number of days the subject experience no seizures over the double-blind assessment phase.

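### The percent reduction from exp(difference) − 1 is described as a reduction in the 28-day seizure rate, but on log(rate + 1) it is a reduction in (rate + 1), and a second formula with a different result shares its name

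*SAP*

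**What the plan says.** SAP section 6.1.1 builds the primary endpoint by adding 1 before taking logs: the quantity 1 "is added to the 28-day seizure rate for all subjects to account for any possible" zero counts. Section 8.1 models that same quantity.

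The log-scale difference d is then turned into a percentage by 100% × [exp(d) − 1]:

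- Section 6.1 (repeated in Appendix 1): a difference of -0.400 "translates into a 33% reduction in the 28-day seizure rate of the pregabalin group from the placebo group".
- Section 8.1: a difference of -0.358 "translates into a 30.1% reduction in the 28-day seizure rate of the pregabalin group from the placebo group".
- Section 2.2, Table 1: the same conversion gives -41.4% and -30.1%, in a column headed "Percent Difference from Placebo". The header does not name the quantity.

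Section 6.1 says the percentage will be calculated on "the two-sided 95% confidence intervals, the least square means and their standard errors", and gives no formula for the standard errors.

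The same places add a second calculation. In section 6.1: "An additional back transformation will be calculated for percent reduction in seizures for each pregabalin treatment group relative to placebo for presentation as follows". In Appendix 1 it "will be calculated for the percent reduction in seizures for each pregabalin treatment group relative to placebo for presentation in the CSR as follows". This one subtracts 1 from each exponentiated LS mean before forming the ratio. Appendix 1 puts both calculations in a single row under one name. The summary table in section 8.5 announces the back-transformed percentage without saying which formula it means.

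**The concern.** Exp(d) − 1 is a percent change in the rate only when the outcome is log(rate). With 1 added, exp(d) is a ratio of two back-transformed values of (rate + 1). A given d then has no single rate reduction attached to it, because the answer depends on the placebo rate. The second formula confirms this by giving a different value whenever d is not zero.

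This is how the size of the primary effect will be stated. As written, the study report would carry two different percentages per dose under one name, and the one described as the reduction in the seizure rate measures something else. When d is negative, that figure understates the reduction in the back-transformed (geometric-type) rate. When d is positive, it understates the increase.

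The wording on standard errors is a smaller hazard of the same kind. Exponentiating a standard error and subtracting 1 gives a number with no useful meaning.

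**Working it through.** **Inputs.** From the SAP: the endpoint log(rate + 1) (6.1.1, 8.1, Appendix 1); d = -0.358 and -0.534 (2.2); d = -0.400 (6.1); SD 0.67 and 56 subjects per group (2.2). Assumed: R, the back-transformed placebo rate per 28 days, exp(LS mean) − 1, which the documents do not give. d is held fixed while R varies.

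**1. Reproducing the SAP's figures.** 100 × [exp(d) − 1] gives -30.1% for -0.358, -33.0% for -0.400 and -41.4% for -0.534. All agree with the SAP.

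**2. What that figure measures.** Write R₁ for the back-transformed pregabalin rate. Then exp(d) = (R₁ + 1)/(R + 1), so exp(d) − 1 is the relative change in (rate + 1).

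**3. The second formula.** R₁ = exp(d)(R + 1) − 1, so

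(R₁ − R)/R = [exp(d) − 1] × (R + 1)/R.

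For d = -0.358 and R = 3: R₁ = 0.6991 × 4 − 1 = 1.796, and (1.796 − 3)/3 = -40.1%, against -30.1% from the first formula.

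| d | First formula | Second, R = 3 | R = 5 | R = 10 | R = 20 |
|---|---|---|---|---|---|
| -0.358 | 30.1% | 40.1% | 36.1% | 33.1% | 31.6% |
| -0.400 | 33.0% | 44.0% | 39.6% | 36.3% | 34.6% |
| -0.534 | 41.4% | 55.2% | 49.6% | 45.5% | 43.4% |

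For -0.358 the gap is 10.0, 6.0, 3.0 and 1.5 points across the row. For -0.534 it is 13.8, 8.3, 4.1 and 2.1 points. Below R = 3 it grows quickly: at R = 1 the second formula gives 60.2% for -0.358 and 82.7% for -0.534.

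**4. Standard errors.** SE(d) = 0.67 × √(2/56) = 0.1266. Putting this through exp(x) − 1 gives 13.5%. The delta-method SE of exp(d) − 1 is exp(d) × SE(d): 0.6991 × 0.1266 = 8.9 points for -0.358, and 0.5863 × 0.1266 = 7.4 points for -0.534.

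**5. Intervals.** For the first figure, exponentiating the limits d ± 1.96 × 0.1266 and subtracting 1 is valid. For the second it is not enough, because that figure depends on both LS means. As an illustration, the two LS means were simulated as independent normals with SE 0.67/√56 = 0.0895, with rates bounded at zero:

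| d | (rate + 1) interval | Rate interval, R = 3 | Rate interval, R = 10 |
|---|---|---|---|
| -0.358 | -45.5% to -10.4% | -58.5% to -14.5% | -49.5% to -11.5% |
| -0.534 | -54.3% to -24.9% | -69.9% to -34.7% | -59.0% to -27.7% |

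**6. Arithmetic mean rates.** Neither formula is the reduction in the mean rate. If log(rate + 1) is normal, a group's mean rate is exp(mean + SD²/2) − 1. With R = 10, d = -0.358 and placebo SD 0.67, the reduction in the mean is 32% if the active SD is also 0.67, and 25% if it is 0.80. The labelled 30.1% can lie on either side.

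**The case against.** The strongest reply is that the SAP has already dealt with this. The rate-scale formula is written out in full, it is introduced as an additional calculation, and the amendment log explains that it follows a regulator's request in a related study. Section 8.1 also plans raw-rate summaries and supplemental models in which a "canonical log link function will be applied to the raw seizure counts", with no 1 added. Decisions rest only on the log scale, and the gap depends on a placebo rate that the documents do not give: at R = 20 it is only 1.5 points for -0.358. The second formula is not the reduction in mean rates either.

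Much of this stands. No analysis is missing, no test changes, and the size of the gap is conditional on R. Two narrower points also stand: Table 1 names no quantity, so it is unclear rather than wrong; and no interval is expressly planned for the second formula, so an interval method matters only if one is shown.

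It does not remove the fault. Planning the correct rate-scale figure leaves the first one still described as the rate reduction, beside a different number with the same name. The supplemental models do not relabel the primary result. Low rates cannot be set aside either, since the SAP adds 1 precisely because zero counts can occur.

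**Conclusion.** The concern holds. On log(rate + 1), the figures of 30.1% and 33% are reductions in (rate + 1), and sections 6.1 and 8.1 and Appendix 1 describe them wrongly. The second formula differs from the first by the factor (R + 1)/R.

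The mislabelling follows from algebra and needs no assumption. Its size does need one: for the two planning differences the gap is about 3 to 14 points for assumed placebo rates of 3 to 10 per 28 days, smaller above that range and larger below it. Saying that the labelled figure understates the effect applies only to the back-transformed rate; the direction against the arithmetic mean rate is unknown.

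Hypothesis tests, p-values, power, sample size and log-scale intervals are unaffected. The change should be made because it concerns the stated size of the primary effect and is cheap.

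**What to change.** 1. In sections 6.1 and 8.1 and Appendix 1, label exp(d) − 1 and its back-transformed confidence interval as the percent reduction in (28-day rate + 1). Label the second formula as the percent reduction in the back-transformed 28-day rate. State that the two differ by definition. Name the quantity in the Table 1 header.
2. Report standard errors on the log scale, or state that a delta-method standard error is used for the percentage.
3. If the second figure is shown with an interval, derive it from both LS means and their covariance by a method that stays valid at low rates, for example a subject-level bootstrap with the back-transformed rate bounded at zero. Avoid a delta interval on the percent scale, or a log rate-ratio interval, when either arm's back-transformed rate is near zero.

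Two editorial points can be settled in the same edit: section 8.1 calls the between-arm result a reduction from baseline, and section 8.5 should name the formula it means. The log-scale tests stay as they are.

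Items 1 and 2 cost SAP wording and table labels; the report will show two differently named percentages per dose and need a footnote. Item 3 costs some programming if it is used. In the illustration for -0.358, the interval is 44.0 points wide at R = 3 and 37.9 at R = 10, against 35.1 for the (rate + 1) interval. For -0.534 it is 35.2 and 31.3 against 29.4. Much of that is a change of scale, since the point estimate grows too; it is not lost precision.
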